#### Screening and Eligibility

Subjects who consent may be screened if they have a known case of CT or GC within 16 weeks of enrollment, or suspicion of current CT or GC infection (subsequently confirmed with NAAT test at Screening Visit). Subjects randomized within 45 days of initial screening do not need to be re-screened.

#### **Intervention and Follow-up Period**

The intervention period is defined as Visits 1 to 5. There is one follow-up visit (Visit 6) 4 weeks after the last intervention visit. These periods are outlined in the Schedule of Assessments (Table 1). The protocol-defined period of observation is 20 weeks.

### Safety Follow-up After Protocol-defined Period of Observation

This period includes safety follow-up as required by Good Clinical Practice (GCP) and standard clinical study practice. Adverse events (AEs) determined to be at least possibly related to the investigational product continuing after the final study visit (Visit 6) will be followed until resolution or stable status as determined by the Investigator. Applicable information is found in Section 6.3.

## 2.1 Study Outcome Measures

#### 2.1.1 Primary Outcome Measures

The primary objective of this study is to demonstrate the superior efficacy of AMPHORA compared with placebo for the prevention of urogenital CT infection. The primary efficacy endpoint is the proportion of subjects who experience at least one CT infection during the study intervention period (incident infection of CT).

## 2.1.2 Secondary Outcome Measures

The secondary outcome will measure the proportion of subjects who experience at least one urogenital GC infection during the study intervention period (incident infection of GC).

#### 2.1.3 Exploratory Outcome Measures

Exploratory assessments include:

- AMPHORA usage during the study (rate of product use adherence) and sensitivity analyses of the primary parameter (proportion of subjects who experience at least one CT or GC infection during the study intervention period) and subjects with ≥20%, ≥40%, ≥60%, ≥80%, and 100% product use adherence
- Assessing subject satisfaction (including sexual satisfaction) with AMPHORA over the course of the clinical study

## 2.2 Study Population

Approximately 1055 women who have had a documented CT or GC vaginal infection at any time over the 16 weeks preceding enrollment, or suspicion of current CT or GC infection (subsequently confirmed with NAAT test at Screening Visit), will be screened to identify 844 healthy female subjects who are eligible to participate.

## 2.3 Study Schedule

**Schedule for individual subjects:** Individual subjects will participate in the study for up to 24 weeks. The study Schedule of Assessments (Table 1) and the description of procedures involving study subjects, by study visit, is provided in Section 5.8.

# 3 Study Enrollment and Retention

No study procedures will be performed until informed consent is obtained. Eight hundred forty-four (844) healthy female subjects, ages 18 to 45, will be enrolled.

Subjects will be recruited through institutional review board (IRB)-approved materials, database queries, and word of mouth. Children, pregnant women, prisoners, and other vulnerable populations will not be enrolled.

Screening will begin with the Investigator or designee providing an overview of the study to the potential subject. Subjects will be excluded if they do not understand the protocol and participation requirements and/or if they are unable, unlikely, or unwilling to comply with gel application as directed, eDiary recording, or follow-up visit attendance. All subjects who consent will be assigned a screening number.

All eligibility criteria must be met for inclusion into the study; no waivers will be granted.

In this study, subjects will be encouraged to strive for 100% product use adherence; however, emphasis will be placed on accurate and forthright eDiary recording of each coital event noting use or non-use of the product and any circumstance that may have impacted their decision to use or not use as directed under the study. Adherence to product use will be measured using a combination of eDiary reporting and number/inspection/staining of returned investigational product/gel applicators.

Study retention strategies will include clear explanations during enrollment of the study schedule and procedures and financial payment and/or reimbursements. Study staff will be actively involved in engaging subjects and implementing systems for appointment reminders and follow-up with missed visits.

#### 3.1 Inclusion Criteria

- 1. Healthy female subjects between 18 and 45 years of age, inclusive
- 2. Ability to understand the consent process and procedures
- 3. Subjects agree to be available for all study visits
- 4. Written informed consent in accordance with institutional guidelines
- 5. Negative pregnancy test
- 6. Negative CT and GC NAAT at screening or positive CT or GC NAAT and receives SOC treatment prior to enrollment
- 7. Agree to use a woman-controlled method of contraception that is not directly delivered to the vaginal mucosa (with the exception of a vaginal ring) throughout the duration of the study, such as oral contraceptives, birth control implants, intrauterine

- devices (IUDs), or tubal ligation. Condom use only is not an acceptable form of contraception for this study
- 8. Able and willing to comply with all study procedures
- 9. Documented (as part of a retrievable medical record) CT or GC infection within 16 weeks prior to enrollment. Acceptable documentation will include:
  - Lab reports confirming CT/GC infection OR
  - Third party clinic note confirming previous CT/GC infection and indicating the date of diagnosis and/or date of treatment
- 10. Reports vaginal sexual intercourse with a male partner at least three times per month in the previous month and anticipates vaginal sexual intercourse regularly for the duration of the study
- 11. Agree to abstain from douching or any form of vaginal suppository use (other than investigational product) during course of study

#### 3.2 Exclusion Criteria

- 1. Participation in any study with an investigational compound or device within 30 days prior to signing informed consent
- 2. In the opinion of the Investigator, has a history of substance or alcohol abuse in the last 12 months
- 3. In the opinion of the Investigator, has issues, conditions, or concerns that may compromise the safety of the subject, impact the subject's compliance with the protocol requirements, or confound the reliability of the data acquired
- 4. Is an Evofem, ICON GPHS, or clinical site employee regardless of direct involvement in research activities, or their close relative
- 5. Pregnant (or actively trying to become pregnant), or breastfeeding
- 6. Women who have undergone a total hysterectomy (had uterus and cervix removed)
- 7. Inability to provide informed consent
- 8. Has a history or expectation of noncompliance with medications or intervention protocol
- 9. Has engaged in sexual vaginal intercourse or douching, or used any form of vaginal suppository or intravaginal device (with the exception of contraceptive vaginal ring or tampons) for 24 hours prior to enrollment (may be enrolled at a later date if all other criteria are met)
- 10. Menstruating at enrollment (may be enrolled at a later date if all other criteria are met)
- 11. Is currently being treated, or have been treated, for a period of 21 days prior to enrollment, with specific antibiotics known to be used for the treatment of CT or GC:
  - Azithromycin

- Erythromycin
- Tetracycline
- Minocycline
- Doxycycline
- Levofloxacin
- Ofloxacin
- Ceftriaxone
- Cefixime
- 12. In the opinion of the Investigator, has signs/symptoms that indicate persistence of chlamydia or gonorrhea infection diagnosed at screening, new interval infection and/or a failure to comply with or complete the prescribed treatment regimen following a positive screening NAAT
- 13. Women who regularly use douches, vaginal medications, products, or suppositories
- 14. Women who are currently using contraceptive products that are directly delivered to the vaginal mucosa, such as diaphragms, spermicides, or any vaginally applied or inserted products containing N-9
- 15. Children, pregnant women, prisoners, and other vulnerable populations

#### 3.3 Prohibited Medications

Subjects must not be currently taking or applying, or have taken or applied, for a period of 21 days prior to enrollment, antibiotics with activity against CT or GC. The following antibiotics meet these criteria:

- Azithromycin
- Erythromycin
- Tetracycline
- Minocycline
- Doxycycline
- Levofloxacin
- Ofloxacin
- Ceftriaxone
- Cefixime

#### 3.4 Randomization

This is a Phase 2B/3 placebo-controlled randomized study with 422 subjects per intervention arm, for a total of 844 subjects. The 844 subjects will be randomized using an Interactive Web Response System (IWRS) in a 1:1 fashion across the two intervention groups, AMPHORA or

placebo. Randomization will be stratified by site, and all documentation of this procedure and output will be saved with the IWRS vendor until the end of the study. Randomization will occur following enrollment and prior to issuance of investigational product to subjects.

#### 3.5 Blinding

Investigators and subjects in both intervention groups will remain blinded to their intervention assignment (AMPHORA or placebo) over the entire duration of the study (double-blind). The Sponsor, Evofem, Inc., will prepare the investigational product as well as placebo and supply these products in ready-to-dispense status.

Any request from the Investigator for information about treatment administered to study subjects must be approved by the Medical Monitor.

If the code must be broken in the case of an emergency for subsequent management of a subject, the Investigator must provide a written request with record of the circumstances surrounding the event, including the purpose, date, and personnel involved. Emergency unblinding will be available by using the IWRS. An emergency treatment disclosure is a reportable event that must be reported to the Medical Monitor within 24 hours of the event.

Otherwise, blinding will not be broken until all subjects have completed the final study visit and the database has been locked and approved.

#### 3.6 Withdrawal

#### 3.6.1 Reasons for Withdrawal

A study subject will be discontinued from participation in the study for:

- Development of any exclusion criteria
- Positive GC/CT NAAT testing at enrollment
- Pregnancy or breastfeeding
- Request by subject to terminate participation
- Subject is no longer sexually active on a regular basis, ie, records no sexual activity for two or more cycles
- Requirement for prohibited treatment (see exclusion criteria) during the intervention period
- Intervention-related toxicity
- Lost to follow-up
- Request of primary care provider

- Request of the IRB/ethics committee, US Food and Drug Administration (FDA), or Sponsor
- Subject is no longer able to attend study visits and/or comply with study procedures
- The subject's well-being, based on the opinion of the Investigator

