#### TREATMENT DURATION:

After a screening period of up to 45 days, women will be randomized to receive either AMPHORA or placebo. Each woman will participate in the study until after she has completed 16 weeks of treatment. The final visit to the clinical site will take place 4 weeks after the end of treatment even if the subject discontinues treatment prematurely

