#### 8.2 Sample Size Considerations

The primary analysis is a comparison between proportion of subjects who experience at least one CT infection among the intervention groups (AMPHORA or placebo).

It is assumed that the proportion of subjects experiencing at least one infection of CT during the study period (incident infection of CT) up to Week 16 under placebo will be 22.5%. An incident infection of CT of 13% in the subjects receiving active treatment (ie, a treatment difference of 9.5%) is considered clinically relevant for AMPHORA versus placebo. Using a Chi-square test for the primary endpoint, 253 analyzable subjects per treatment group (506 subjects total in the ITT population) will yield approximately 80% power to detect 9.5% treatment difference with a 2-sided 5% type I error rate (SAS 9.3 PROC POWER). Assuming that 20% of the total enrolled subjects will be lost to follow-up, 15% will be re-infected with GC (making them ineligible for the primary endpoint analysis), and 5% will be deemed ineligible for analysis due to antibiotic use, the total sample size planned for this study is 844 subjects.

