### **Important Use Information**

- During your entire time in this study, use the Study Drug every time you have vaginal sex regardless of the time of the last application or even if you have sex more than once in a day. The Study Drug can be used immediately before or up to one hour before vaginal sex.
- If you or your partner develop burning or irritation of the vagina or penis or experience difficult or painful urination, discontinue use and consult your clinical site staff.

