7.3 Analysis Eligible Subjects

When considering subjects for inclusion in the re-infection analyses, it becomes apparent that some are not appropriate for consideration. As an example, if a subject is treated with an antibiotic for an illness and this antibiotic also treats GC and/or CT, then it is not possible to get a true reflection as to the re-infection prevention abilities of the product under investigation. Likewise, if a subject is found to be infected with GC and needs to be treated, the ability to later detect a CT infection is compromised. As such, for subjects to be eligible for CT (or GC) re-infection analyses, we require the following:

- 1) Known re-infection status through the end of the treatment phase (i.e., a determination of positive or negative re-infection can be definitively made per definitions below),
- 2) No use of prohibited antibiotic medications, and
- 3) No GC (or CT) re-infection, unless it is identified at the same time as the CT (or GC) re-infection.

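### Toxicity is a reason to leave the study, with no route to stop the gel and keep CT/GC testing to Week 16, so outcomes that could be collected are lost

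*Protocol*

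**What the plan says.** Protocol Section 3.6.1 opens with "A study subject will be discontinued from participation in the study for" and includes "Intervention-related toxicity" in the list, without a grade. The leaflet in Appendix C tells women: "If you or your partner develop burning or irritation of the vagina or penis or experience difficult or painful urination, discontinue use", and to consult site staff. It does not mention leaving the study.

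After withdrawal, three places govern testing:
- Section 3.6.2 and Table 1 footnote 3 apply Visit 5 procedures, with a NAAT, at an Early Termination visit. Section 5.10 makes that visit depend on the woman's willingness.
- Section 3.6.2 encourages one post-intervention visit with Visit 6 procedures.
- The Synopsis (Treatment Duration) ties that visit to the end of treatment, not to Week 20: "The final visit to the clinical site will take place 4 weeks after the end of treatment even if the subject discontinues treatment prematurely".

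For the primary endpoint, Protocol 8.3.3 analyses women infected with CT and women who complete without re-infection. For an uninfected woman, Section 3.7 defines completion as finishing all visits. SAP 7.3 item 1 requires "Known re-infection status through the end of the treatment phase". SAP 8.8.1 counts any positive NAAT at Visits 1 to 5 as an event, and requires negatives at Visits 1 and 5, with no positive between, for a non-event. Protocol 8.3.3 rules out imputation.

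**The concern.** The plan treats stopping the product and leaving the study as one act when the reason is toxicity. A woman who stops at Week 5 would have her last planned test at about Week 9 (5 + 4), although she could still attend and give a self-collected swab at the later visits. A positive result at that last visit would carry the Visit 6 label, outside the Visits 1 to 5 that define an event.

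The rest of the design keeps non-users under follow-up. Protocol Section 3 asks women to record use and non-use honestly, and the SAP analyses adherence bands down to 20%. A woman who simply does not use the gel can therefore stay, while one who stops because of toxicity leaves.

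This loss of outcome data is a consequence of the assigned gel. If it differs between arms, the randomised comparison is disturbed, and no analysis can recover swabs that were never taken.

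**Working it through.** **1. The plan's own figure.** Inputs from Protocol 8.2: CT proportion "up to Week 16 under placebo will be 22.5" per cent; 13% on AMPHORA; "2-sided 5% type I error rate"; "approximately 80% power to detect 9.5% treatment difference".

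n per arm = [1.960·√(2·0.1775·0.8225) + 0.8416·√(0.225·0.775 + 0.13·0.87)]² / 0.095² = 252.7, so 253. Power at 253 is 80.04%. Adding the three losses, 20% + 15% + 5% = 40%, gives 506/0.60 = 843.3, so 844. The plan's figures reproduce. Toxicity withdrawal is not among the named losses, unless it is meant to sit inside the 20%.

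**2. Who is lost.** A woman with a positive CT NAAT by early termination is an event and stays in. A woman without one does not finish all visits and has no Week 16 result, so the loss falls on women with no positive test.

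**3. Illustration.** The documents give no toxicity rate, so the following are assumptions: planned risks, constant hazard, a share s of the AMPHORA arm only stops at Week 4, placebo hazard afterwards, Early Termination NAAT attended, positives kept.

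- Hazards over 16 weeks: h₁ = −ln(0.87) = 0.1393; h₀ = −ln(0.775) = 0.2549.
- Positive by Week 4: e = 1 − exp(−0.25·h₁) = 3.42%.
- A stopper's 16-week risk: 1 − exp(−(0.25·h₁ + 0.75·h₀)) = 20.2%.
- All women assigned: AMPHORA proportion = (1−s)·13% + s·20.2%.
- Plain reading of the plan (early negatives dropped): [(1−s)·13% + s·e] / [(1−s) + s·e].
- Early negative counted as Visit 5: (1−s)·13% + s·e.

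Difference from placebo (22.5%), in points:

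| s | All assigned | Early negatives dropped | Early negatives counted as Visit 5 |
|---|---|---|---|
| 5% | 9.14 | 9.34 | 9.98 |
| 10% | 8.78 | 9.17 | 10.46 |
| 15% | 8.42 | 8.98 | 10.94 |

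On the plain reading the gap from the all-assigned figure is 0.20, 0.39 and 0.56 points. On the Visit 5 reading it is 0.84, 1.68 and 2.52 points, because 4 weeks of follow-up are counted as 16.

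**4. Direction.** Take no true effect (22.5% in both arms) and assume withdrawal of 10% on AMPHORA and 2% on placebo.

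- Positives kept, negatives dropped, exit at mid-period: infected by then = 1 − 0.775^0.5 = 11.97%. AMPHORA reads (0.9·0.225 + 0.1·0.1197)/(0.9 + 0.1·0.1197) = 23.5%; placebo reads 22.7% by the same formula. That is a spurious AMPHORA disadvantage of 0.8 points.
- All withdrawn women dropped, their risk 35%: AMPHORA (0.225 − 0.1·0.35)/0.9 = 21.1%; placebo (0.225 − 0.02·0.35)/0.98 = 22.2%. That is a spurious benefit of 1.1 points, with two-sided type I error about 6.0%. If their risk is 10%, the bias is 1.1 points the other way; at 22.5% it is zero.

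**5. Numbers.** 1% of 844 is 8.4 randomised women; with the 60% the plan expects to be analysable, 8.4 × 0.60 ≈ 5.

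**The case against.** The best defence is that the plan does not abandon these women. It schedules a NAAT at early termination and offers a further visit, and it keeps women who are CT-positive by early termination. A reader might infer that every woman who stops for toxicity disappears from the primary comparison. The documents do not support that, and keeping the positives roughly halves the distortion on the plain reading: at s = 10%, 0.39 points against 9.50 − 8.78 = 0.72 if all stoppers were dropped.

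Nor is exclusion of the remaining women certain. Protocol Table 1 gives Visit 5 and Early Termination a shared column, so a negative early test might be taken as the Visit 5 result. SAP 7.2, on missing data, was not in the text available for this review and could contain a rule. It could not supply swabs that were not taken.

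A reader might also infer contradictions. Appendix C is an instruction to stop and contact the site, and Section 6.5 covers reporting and follow-up of severe events. Both are silent on participation. The Synopsis timing is compatible with Section 3.6.2. The fault is a gap: no passage says what stopping product means for staying in the study.

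Finally, more exits on AMPHORA can only be inferred from its acid-buffering pH of 3.5 against a non-buffering placebo at pH 4.5 (Section 4.1). No toxicity or discontinuation rate is given for either gel.

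**Conclusion.** The point holds as a modest weakness in data collection. Toxicity leads to study exit, and a woman with no positive test then lacks the Week 16 result that the primary analysis calls for. If her early negative is dropped, the illustration puts the distortion at 0.2 to 0.6 points for 5% to 15% stopping in the AMPHORA arm alone. If it is counted as Visit 5, the distortion is larger, 0.8 to 2.5 points. The available SAP text does not choose between these readings.

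A reader might infer that the rule flatters AMPHORA. The documents do not establish that: the sign depends on which women leave, when, and how their early tests are counted. The sizes rest on assumed stopping rates, constant hazard and placebo risk after stopping. On the plain reading the effect is small unless stopping is frequent and unequal. Each 1% stopping in both arms removes about 5 analysable women, or none extra if these exits already sit within the 20% loss allowance.

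**What to change.** - In Protocol 3.6.1, separate reasons to stop study product from reasons to leave the study.
- State that a woman who stops product for toxicity and has not withdrawn consent is asked to continue the scheduled Visits 2 to 5 NAATs and the eDiary to Week 16, with the date and reason for stopping recorded.
- In SAP 7.3 and 8.8.1, state that a negative early-termination NAAT before Week 16 is not a Visit 5 result.
- Reconcile the Synopsis (Treatment Duration), Sections 3.6.1 and 3.6.2, and Appendix C on what stopping product means for participation. The clinical threshold for stopping is left to the sponsor.

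The cost is amendment wording and a short SAP edit. The visits and self-collected swabs are already in the schedule. Some women who have stopped the gel would be asked to attend up to three more visits: at most Visits 2 to 6 (five) in place of an Early Termination visit and one follow-up (two).

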#### 3.6.2 Handling of Withdrawal

If a subject is withdrawn from participation, the reason(s) for discontinuation must be documented in the source documents and electronic case report forms (eCRFs). The procedures for Visit 5 should be followed for the Early Termination Visit. Subjects who withdraw or are withdrawn from the study who received any amount of the investigational product will be encouraged to return to the clinic for a final visit to complete the post-intervention follow-up visit (all procedures from Visit 6). If an AE or serious adverse event (SAE) has occurred, every effort will be made to undertake protocol-specified safety follow-up procedures, and the subject will be encouraged to receive appropriate care under medical supervision until the symptoms of any AE resolve or the subject's condition becomes stable.

#### 3.6.3 Handling Subjects Lost to Follow-up

The study design has incorporated primary, secondary, and tertiary strategies for reducing the number of subjects lost to follow-up. Primary strategies include having sites: 1) fully inform subjects of study visit details prior to randomization, 2) addressing subjects' expectations on study participation, 3) motivating subjects to adhere to follow-up visits and research protocols, and 4) utilizing eDiaries for data entry and review. Secondary strategies include: 1) scheduling all visits around subjects' availability which are within the visit window, 2) providing a visit reminder ahead of time, and 3) reviewing data for missed and overdue follow-up visits. Tertiary strategies include: 1) discussing subjects' difficulty in adhering to study protocol and answering any questions they might have and 2) continuing attempts to reach subjects lost to follow-up and recording all contact attempts.

A subject will be considered as lost to follow-up if participation in study activities is not continued after:

- Three attempts at telephone contact without success following missed study assessment timepoint, followed by
- Issuance of a certified letter to last documented address of subject, and no response within 7 days of mailing

Documentation of lost to follow-up status will be maintained in the subject's case report form (CRF) and in source documents. The reason(s) for the lost to follow-up, if known, and the appropriate timelines for subject-study site correspondence will be captured along with the study site's attempts to reach the subject. Lastly, all proper procedures of sending certified letter of

Protocol: EVO-003

discontinuation from study based on lost to follow-up status and a recommendation to come in for a discontinuation visit to determine safety of the subject will be followed by the study site. The conditions and plans for replacement of subjects lost to follow-up are described in Section 3.6.3.

